### **Objectives**

Primary objective

To study the effectiveness of a reduced corticosteroid schedule for the treatment of a relapse in children with steroid sensitive nephrotic syndrome.

Secondary objectives

- To study the influence of maintenance immunosuppressive therapy on the effectiveness of a reduced steroid schedule for the treatment of a relapse in children with steroid sensitive nephrotic syndrome. Maintenance immunosuppressive therapies include levamisole, cyclosporine, tacrolimus, mycophenolate mofetil and mycophenolate sodium, and alternate day prednisolone with a maximum of 4 mg/m^2;
- To investigate the occurrence of relapses, frequency of relapses and progression to steroid dependent and frequent relapsing nephrotic syndrome in children with nephrotic syndrome under the standard treatment regimen;
- To study the influence of maintenance immunosuppressive therapy on the occurrence of subsequent relapses, frequency of subsequent relapses and progression to steroid dependent and frequent relapsing nephrotic syndrome under the standard regimen, and;
- To study the effectiveness of a reduced steroid schedule for the treatment of a relapse and occurrence and frequency of subsequent relapses in children with steroid dependent nephrotic syndrome.

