### Baseline patient characteristics

Discrete variables will be demonstrated by frequencies and percentages. Continuously distributed variables will be demonstrated using either mean  $\pm$  standard deviation for data with normal distribution, or median and interquartile range for non-normally distributed data.

Table 2: Participant baseline characteristics

	Standard treatment (n = xxx)	Placebo (n = xxx)
Participant characteristics		
Male, n (%)	n/N (%)	n/N (%)
Age, years; median (IQR)	xx.x (xx.x to xx.x), n	xx.x (xx.x to xx.x), n
Age at onset, years; median (IQR)	xx.x (xx.x to xx.x), n	xx.x (xx.x to xx.x), n
Descent, n (%)	n/N (%)	n/N (%)

- Caucasian - Asian - African - Other, specify		
Maintenance therapy, n (%) - Levamisole - Cyclosporine - Tacrolimus - Mycophenolate mofetil - Mycophenolate sodium - Prednisolone	n/N (%)	n/N (%)
Total number of relapses prior to study participation	n/N (%)	n/N (%)
Number of relapses in preceding 24 months	n/N (%)	n/N (%)

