## ANALYSIS

### Outcome definitions

#### Primary outcome

##### Time to first relapse

- Definition: time to first relapse (=first day of treatment of the next relapse) after the final prednisolone dose. The final prednisolone dose represents the beginning of study medication for the placebo group and the end of study medication for the prednisolone group.
- Timing: censored at 12 and 24 months
- Measurement value: days

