### **Analysis methods**

#### Primary endpoint

##### Time to first relapse after the final prednisolone dose

- As normal distribution is not assumed, the median time to relapse will be compared between the groups using a Mann-Whitney test;
- In case patients did not experience any relapse after 24 months or patients are lost to follow up before they experienced a relapse, incidence rates or person-time rates will be used to compare the groups;
- If a normal distribution is shown in the Shapiro-Wilk W test, a *t* test will be used;
- The percentages of study subjects with a relapse at 12 and 24 months will be compared between the groups;
- The cumulative probability on the absence of a relapse will be estimated by survival analysis, according to the Kaplan-Meier method. Log-rank tests are used for the comparison between the standard treatment group and placebo group;
- To test for the influence of factors, such as the use of maintenance immunosuppressive therapy, logistic regression analysis for nephrotic syndrome relapses with covariate analysis will be performed;
- Within each subject time to relapse after study medication will be compared to time to relapse before entering the study using a paired sample *t* test. This test will exclusively be performed in patients without changes in maintenance therapy.

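### The SAP specifies no analysis of whether maintenance therapy modifies the effect of the reduced schedule, and its logistic model ignores relapse timing and censoring

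*SAP*

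**What the plan says.** The SAP's Objectives section lists as its first secondary objective "To study the influence of maintenance immunosuppressive therapy on the effectiveness of a reduced steroid schedule for the treatment of a relapse". A separate secondary objective is "To study the influence of maintenance immunosuppressive therapy on the occurrence of subsequent relapses" under the standard regimen.

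The Outcome definitions section defines the primary endpoint as "time to first relapse (=first day of treatment of the next relapse) after the final prednisolone dose", with "Measurement value: days" and "Timing: censored at 12 and 24 months".

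Under Analysis methods, Primary endpoint, the influence of factors such as maintenance therapy is handled in one sentence: "logistic regression analysis for nephrotic syndrome relapses with covariate analysis will be performed". It names no horizon (12 or 24 months), no covariates, no treatment term and no interaction. Kaplan-Meier curves and log-rank tests are planned, but only for one arm against the other.

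Under Secondary endpoints, a Poisson model for relapse rates lists treatment and maintenance therapy as separate variables, together with sex, age and period. The Missing data section rules out imputation and says that available data up to loss or withdrawal will be used. Cox regression is named in the Sample size section and nowhere in the analysis methods.

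**The concern.** There are two faults, and they compound.

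**The question is not matched by an analysis.** "To study the influence of maintenance immunosuppressive therapy on the effectiveness of a reduced steroid schedule" is a question about effect modification: does the contrast between schedules differ between children with and without maintenance therapy? That needs an interaction term or a treatment effect in each stratum. A coefficient for maintenance therapy alone says whether such children relapse more or less often. Reported as its influence on effectiveness, that coefficient would answer a different question.

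**The model does not suit the endpoint.** Logistic regression on relapse yes/no discards the day of relapse and cannot represent censoring. The SAP itself foresees children lost before any relapse. Without imputation, such a child must be dropped, which sits badly with the promise to use data up to loss, or counted as relapse-free, which may be wrong. The SAP does not say which.

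Because horizon and terms are open, the form of the model could also be settled after unblinding.

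**Working it through.** **1. Each planned analysis against the first secondary objective**

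| Analysis | Uses time and censoring? | Effect by maintenance therapy? |
|---|---|---|
| Kaplan-Meier, log-rank | yes | no, arms only |
| Logistic regression | no | none specified |
| Poisson regression | rates, but for number of relapses | listed as separate variables, no interaction |

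No subgroup analysis by maintenance therapy appears elsewhere in the SAP.

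**2. The plan's own figure.** The 72 per group is used below only as the sample size. With SD 120, margin 50 days, power 80% and one-sided alpha 0.05:
n = 2 × (120/50)² × (1.645 + 0.842)² = 71.2, so 72. It reproduces at that alpha.

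**3. Information lost by dichotomising, for the overall treatment effect.** Input from the SAP's Interim analysis section: 30% relapsed at 5.5 months. Assumptions: constant hazard, hazard ratio 1.5, no losses, 72 per arm.

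- Hazard = −ln(0.70)/5.5 = 0.0648 per month.
- Relapse by time t: p0 = 1 − exp(−0.0648t) and p1 = 1 − (1 − p0)^1.5.
- Logistic: z = ln(OR)/SE, with SE² = 1/[72·p0(1 − p0)] + 1/[72·p1(1 − p1)].
- Cox: events D = 72(p0 + p1), and z = √(D/4) × ln 1.5.

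| | 12 months | 24 months |
|---|---|---|
| p0, p1 | 0.541, 0.689 | 0.789, 0.903 |
| ln(OR), SE | 0.631, 0.347 | 0.913, 0.492 |
| z, logistic | 1.82 | 1.86 |
| D | 88.5 | 121.8 |
| z, Cox | 1.91 | 2.24 |
| (z ratio)² | 0.91 | 0.69 |

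At a hazard ratio of 1.25 the information kept is 93% and 77%.

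**4. Detecting the interaction itself.** Simulation of about 600 trials per scenario with 144 children. Assumptions: exponential times, 80% baseline relapse by 24 months, 10% loss, 50% on maintenance therapy with its own hazard ratio of 0.7. Both models were given the interaction term and tested at two-sided 0.05; lost children counted as relapse-free in the logistic model.

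| Treatment HR without / with maintenance | Cox | Logistic |
|---|---|---|
| 1.0 / 1.0 | 6% | 6% |
| 2.0 / 1.0 | 42% | 24% |
| 3.0 / 1.0 | 82% | 28% |

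Part of the logistic shortfall comes from near-empty no-relapse cells, where Wald tests behave poorly. Those cells arise from dichotomising at 24 months.

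**5. What a Cox interaction can deliver.** Assume 80% of 144 relapse, D = 115.2, and a share m is on maintenance therapy. SE of the log ratio of hazard ratios = √[4/(D·m) + 4/(D(1 − m))].

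| m | SE | Ratio detectable at 80% power | Power, ratio 1.5 | Power, ratio 2.0 |
|---|---|---|---|---|
| 0.5 | 0.373 | 2.8 | 19% | 46% |
| 0.3 | 0.407 | 3.1 | 17% | 40% |

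The SAP's 80% relapse figure carries no time horizon, so its use at 24 months is an assumption.

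**The case against.** The strongest defence is that the logistic sentence was never meant for the first objective. It speaks of the influence of factors in general. A main effect on relapse occurrence would suit the separate objective on maintenance therapy under the standard regimen, if fitted within that arm. That is a possible reading, but it leaves the first objective with no analysis at all.

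A reader might infer that the SAP commits to a main-effects model and so excludes the interaction. The text does not go that far. It names no terms, so an interaction is unspecified rather than ruled out.

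A reader might also take the 69% figure to mean that nearly a third of the information on the first objective is lost. It does not show that. It concerns the overall treatment effect, for which the log-rank test already uses timing, and it holds at 24 months only; the SAP fixes neither horizon for the logistic model.

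The Poisson model shows that some adjustment for maintenance therapy and age is planned. It concerns number of relapses and lists no interaction, so it does not fill the gap. Nor does the SAP support calling the Table 2 variables, such as "Number of relapses in preceding 24 months", strong predictors: it lists them without any predictive strength.

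Finally, even Cox regression would detect only a large interaction. This stands, and it governs how the result should be labelled.

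**Conclusion.** The concern holds. The SAP asks an effect-modification question and specifies neither an interaction nor stratum-specific treatment effects to answer it. The model it names for maintenance therapy ignores relapse day and censoring for an endpoint defined by both, and leaves the handling of children lost before relapse open.

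The cost for the overall treatment effect is modest at 12 months (about 9% of the information) and larger at 24 months (about 31%), under constant hazard, a hazard ratio of 1.5 and no losses. For the interaction, the simulated loss at 24 months was larger, but it depends on the assumed share on maintenance therapy, event rate and losses, none of which the SAP gives for this purpose.

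The change should be made. It concerns a secondary objective and does not touch the noninferiority decision. Confidence is high on the missing interaction and the ignored timing, lower on the exact size.

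**What to change.** Replace the logistic model with a Cox model for time to first relapse, containing treatment, maintenance therapy (yes/no), their interaction and baseline covariates named in advance from Table 2, for example age and number of relapses in the preceding 24 months. Use whichever time origin the SAP finally fixes; this point gives no reason to change it. Include a check of proportional hazards.

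Report the treatment hazard ratio with 95% CI in each maintenance stratum and the interaction estimate with its CI. Label the result as estimation, and state that a non-significant interaction is not evidence of equal effects.

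The cost is SAP wording and slightly more analysis work. The variables are already in Table 2, and the Blinding section allows final amendments at the blind review.

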#### Eligibility

- Age over 1 and less than 18 years;
- Steroid sensitive nephrotic syndrome with at least 1 episode of nephrotic syndrome in the preceding 24 months.

This will include the following groups:

- Subjects without maintenance immunosuppressive therapy;
- Subjects with maintenance immunosuppressive therapy:
  - Long term immunosuppressive therapies: levamisole, ciclosporine, tacrolimus, mycophenolate mofetil (Cellcept®), mycophenolate sodium (Myfortic®), prednisolone max. 4 mg/m^2 on alternate days
  - Cyclophosphamide (oral or intravenous), at least three months post completion of therapy
  - A single dose or course of intravenous rituximab, at least three months post completion of therapy
- The last prednisolone use (at a dose over 10 mg/m^2 on alternate days) for the treatment of a previous episode was at least 4 weeks ago.

- Subjects experience a relapse nephrotic syndrome, defined as Albustix positive proteinuria (3+ or higher) for three consecutive days or the presence of generalized edema plus 3+ proteinuria on a single occasion.

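### The before-versus-after paired t test compares two relapse intervals selected and censored by different rules, so it can show a change when there is none

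*SAP*

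**What the plan says.** The last of the seven analyses listed for the primary endpoint (SAP, Analysis methods) is a paired t test: "Within each subject time to relapse after study medication will be compared to time to relapse before entering the study". It is limited to a subset: "This test will exclusively be performed in patients without changes in maintenance therapy". The SAP does not define where the before interval starts, does not say whether the test is run by arm or on both arms together, and does not date the therapy changes that exclude a child.

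Three other parts of the SAP determine what the two intervals can be:

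- **Entry (Eligibility).** Every child enters at a relapse: "Subjects experience a relapse nephrotic syndrome". The last prednisolone above a stated dose "for the treatment of a previous episode was at least 4 weeks ago". The child must also have "Steroid sensitive nephrotic syndrome with at least 1 episode of nephrotic syndrome in the preceding 24 months".
- **Follow-up (Outcome definitions, Time to first relapse).** "Timing: censored at 12 and 24 months". No lower limit applies.
- **Children without a relapse (Analysis methods).** The SAP expects them: "In case patients did not experience any relapse after 24 months or patients are lost to follow up before they experienced a relapse". Its remedy, person-time rates, is given for comparing the groups and not for the paired test. Missing outcomes are not imputed (Missing data).

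**The concern.** A paired t test reads a non-zero mean difference as a change within children. That holds only if, with no change, the two intervals would have the same expected value. Here they would not. The before interval is observed in full for every child because a relapse is the ticket of entry, and the 4-week rule removes its shortest values. The after interval keeps its shortest values and loses its longest to censoring. A t test has no means of using a censored value, so relapse-free children must either be left out or be given a stand-in value. The SAP leaves that choice open.

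The test sits under the primary endpoint, and the SAP calls any p-value below 0.05 statistically significant. A spurious lengthening could be read as support for the reduced schedule, and a spurious shortening as evidence against it.

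**Working it through.** The SAP gives no figure for this test, so there is none to reproduce. The check asks what the test returns when nothing has changed in any child.

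**Inputs from the SAP:** 30% relapsed at 5.5 months (Interim analysis); the 4-week rule and the 24-month episode rule (Eligibility); censoring at 24 months, taken as 730 days; N = 144; p < 0.05, taken as two-sided.

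**Assumptions:** exponential intervals; optional gamma frailty of variance 0 to 1 between children; the before interval counted from the last treatment-dose prednisolone and limited to 28-730 days (the index relapse does not count as the qualifying episode); both arms pooled.

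**Step 1, rate.** With 5.5 months = 167.4 days, rate = -ln(0.70)/167.4 = 0.00213 per day, so 1/rate = 469.4 days. The share relapse-free at 730 days is exp(-730 x rate) = 0.211, so 78.9% relapse. This is close to the 80% with at least one relapse in the Sample size section.

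**Step 2, mean before interval, 28-730 days.** The window is 702 days wide and exp(-702 x rate) = 0.2241. Mean = 28 + 469.4 - 702 x 0.2241/0.7759 = 294.6 days.

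**Step 3, mean after interval.**

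- Relapse-free children dropped: 469.4 - 730 x 0.2111/0.7889 = 274.0 days. Difference: 274.0 - 294.6 = **-20.6 days**.
- Relapse-free children entered at 730 days: 0.7889 x 469.4 = 370.3 days. Difference: 370.3 - 294.6 = **+75.7 days**.

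**Step 4, false positives without frailty.** The variance of an exponential limited to a window of width L is 1/rate² - L² x q/(1-q)², with q = exp(-L x rate). The SDs are 192 days before and 199 days after (relapsers only), so the SD of the difference is √(192² + 199²) ≈ 276. With children entered at 730 days, the after SD is 256.5 and the SD of the difference is about 320.

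- Dropped: n = 144 x 0.789 ≈ 114; SE = 276/√114 = 25.9; 20.6/25.9 = 0.80; rejection ≈ Φ(-1.16) + Φ(-2.76) ≈ **0.13**.
- Entered at 730 days: SE = 320/√144 = 26.7; 75.7/26.7 = 2.84; rejection ≈ Φ(0.88) ≈ **0.81**.
- If run within one arm of 72: 20.6/(276/√57) = 0.56, or about 9%; 75.7/(320/√72) = 2.01, or about 52%.

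**Step 5, range by simulation at N = 144, no true change.**

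| Setting | Mean after minus before | False positives |
|---|---|---|
| 28-730 day before window, relapse-free children dropped | -20 to -23 days | 11-16% |
| Same window, relapse-free children entered at 730 days | +72 to +84 days | 79-92% |
| Same 0-730 day window on both, relapsers only | about 0 | 4.3-5.3% |
| All intervals gamma, mean 185, SD 120; entry limits only | -1 to -5 days | 5-6% |

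In the first two rows, 21-25% of children are relapse-free. The high ends (25%, +84 days) arise when frailty is added without refitting the rate to 30% at 5.5 months; with refitting the figures are 21-22% and +72 to +76 days.

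The third row shows that the false positives come from the unequal rules and not from the t test itself. If the index relapse counts as the qualifying episode, the before interval has no upper limit. With relapsers only, the same exponential and frailty models then give -224 days or more, with at least 96% false positives.

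**The case against.** Much of the case for leaving the test alone is sound.

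- **Dropping relapse-free children is not in itself the bias.** With the same 0-730 day window on both intervals, leaving them out gives a mean difference of about zero. In the dropped scenario the shift comes from the 28-day floor. A reader might infer that the SAP removes the best outcomes, but it does not say that relapse-free children drop out. It leaves their handling open, and the sign of the result turns on it.
- **The maintenance-therapy restriction may be harmless.** The after interval ends at the first relapse, so a change prompted by that relapse comes later, and the restriction may only mean that both intervals were spent on the same therapy. If it also covers changes made after an early relapse, it selects on the outcome. The SAP settles neither the reading nor how often such changes occur, so no size can be attached.
- **Non-normality is a weak ground.** The remark that normality is not assumed concerns the comparison between groups. The t test kept its nominal level when the windows matched.
- **The 50-day limit is not a yardstick here.** It belongs to the difference between arms. The paired test has no margin.
- **The bias can be close to nil.** Under the gamma model with the sample-size mean and SD, almost every child relapses within 24 months and the entry limits hardly matter. Those figures are stated for the first year.

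What remains is that the two intervals follow different rules and that the SAP fixes a significance test on them without saying how censored children are handled.

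**Conclusion.** The point holds for this one supplementary analysis. With no true change, the paired t test can reject well above 5%, in either direction, depending on a choice the SAP does not make: about 11-16% (shortening of 20-23 days) if relapse-free children are dropped, about 79-92% (lengthening of 72-84 days) if they are entered at 730 days. These sizes rest on the exponential or frailty model fitted to 30% at 5.5 months, the 28-730 day before window and pooling of 144 children. Under the gamma model the effect of the entry limits is negligible.

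A reader might infer that the noninferiority conclusion is compromised. The SAP does not support that. The entry rules act alike in both arms, the other comparisons in the same list are between randomised groups, and noninferiority is tied to a confidence interval for the treatment effect, which this test does not supply. The change should be made, but the trial's main result does not depend on it.

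**What to change.** Remove the paired t test as a significance test. At most, report both intervals descriptively by arm, counted from the same origin. The bullet counts from study medication while the primary outcome counts from the final prednisolone dose, a possible 4-week difference in the placebo arm. State the number of relapse-free children beside the figures.

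To use each child's own history, enter the log of the pre-study relapse interval as a baseline covariate in a supportive Cox model of time to first relapse by randomised arm. Censor relapse-free children, and do not exclude any child for a later change in maintenance therapy. State how the pre-study interval is measured.

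The cost is a change of SAP wording, using data that the paired test already needs. The downside is that the before/after comparison no longer carries a p-value and one supportive model is added.

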#### Secondary endpoints

##### Number of relapses after the final prednisolone dose

- Follow-up will be categorized into three periods (period 1, 0-12 months, period 2, 12-24 months, period 3, 0-24 months) and within each period, the number of relapses is counted;
- Poisson regression will be used to evaluate relapse rates in relation to treatment, maintenance immunosuppressive treatment, sex, age and period.

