### **Randomisation**

After prednisolone 60 mg/m^2 daily in 1 dose until complete remission for 3 days, randomisation (allocation ratio 1:1) between:

- Standard treatment: 6 weeks prednisolone 40 mg/m^2 (max. 40 mg) every other day;

- Study treatment: 2 weeks prednisolone 40 mg/m^2 (max. 40 mg) every other day, then 4 weeks placebo every other day.

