### **Sample size**

From previous studies, we know the incidence of nephrotic syndrome in Dutch children to be 1.52/100,000 children/year.[2] Eighty percent of the pediatric patients develop at least 1 relapse of whom 50% continue towards frequent relapsing nephrotic syndrome. Based on data from previous studies, average time to relapse in the first year is approximately 185 days (standard deviation of 120 days).[3] Using the power calculation for a noninferiority trial with a continuous primary outcome, a power of 80% and a noninferiority limit of 50 days, 72 patients per group are required. Using a Cox Proportional Hazard time-to-relapse analysis (survival analysis)[4], similar numbers can be calculated.

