#### Secondary outcomes

##### 1. Number of relapses

- Definition: number of relapses per patient after the final prednisolone dose
- Timing: censored at 12 and 24 months
- Measurement value: number of patients (%)

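### The relapse-count Poisson model has overlapping period levels and no allowance for within-child correlation, so as written its standard errors are too small

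*SAP*

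**What the plan says.** The SAP defines this secondary outcome (Secondary outcomes, item 1) as the "number of relapses per patient after the final prednisolone dose", with cut-offs at 12 and 24 months.

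The analysis (Secondary endpoints, Number of relapses after the final prednisolone dose) has two bullets:

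- The first sets the windows, "Follow-up will be categorized into three periods (period 1, 0-12 months, period 2, 12-24 months, period 3, 0-24 months", and adds that "within each period, the number of relapses is counted".
- The second names the model: "Poisson regression will be used to evaluate relapse rates in relation to treatment, maintenance immunosuppressive treatment, sex, age and period".

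The SAP does not restrict the model to the first two periods or say that it is fitted separately by period. It names no random effect, GEE, robust or clustered variance, dispersion parameter, negative binomial model or person-time offset.

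The Sample size section describes how the disease varies between children: "Eighty percent of the pediatric patients develop at least 1 relapse of whom 50% continue towards frequent relapsing nephrotic syndrome".

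**The concern.** A factor in a regression needs mutually exclusive levels. Here the third level contains the other two. An analyst who follows the text would build three rows per child, with the third count equal to the sum of the first two. Every relapse within 24 months would then be used twice, and three dependent rows would be treated as independent.

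Separately, plain Poisson regression assumes that children with the same covariates share one relapse rate. If rates differ between children, counts from the same child are correlated and 24-month counts vary more than Poisson allows.

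Both faults make standard errors too small. Relapse frequency, and the influence of maintenance therapy on it, are stated secondary objectives, and this is the only model named for relapse counts. Intervals that are too narrow could show a difference in relapse rate that is not there, or give false reassurance about the reduced schedule.

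**Working it through.** **Inputs from the SAP.** Three periods and the covariate list (Number of relapses); 1:1 allocation (Randomisation); 72 children per group (Sample size); significance at P<0.05 and two-sided 95% CIs (Level of confidence intervals and p-values).

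**Assumed inputs.** The SAP gives neither the mean number of relapses per child over 24 months (μ) nor the between-child variance of the relative relapse rate (k). The range tried is μ = 1 to 4 and k = 0 to 1.

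**Reproducing the plan's figure.** The SAP states no figure for the Poisson analysis. The 72 per group is used here only as the number of children. It follows from a 50-day margin, an SD of 120 days, 80% power and one-sided α = 0.05: n = 2 × (1.645 + 0.842)² × 120² / 50² = 71.2, rounded up to 72. How that α fits with the two-sided 95% CI is a separate matter and does not affect this point.

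**Step 1: double counting alone (k = 0).** With D₀ and D₁ relapses in the two arms, the model variance of the log rate ratio is 1/D₀ + 1/D₁. Stacking period 3 turns these into 2D₀ and 2D₁, which halves the model variance but adds no information.

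- True SE / model SE = √2 = 1.41.
- CI width relative to the correct width: 1/1.41 = 0.71, so 29% too narrow.
- Coverage: 2Φ(1.96/1.414) − 1 = 0.834. Type I error: 1 − 0.834 = 16.6%.
- Example with μ = 2: D = 72 × 2 = 144 per arm. The correct SE is √(2/144) = 0.118 and the stacked SE is √(2/288) = 0.083.

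This result needs no assumed relapse rate. Simulation of trials without a treatment effect gave 16.3% and 16.9%.

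**Step 2: adding between-child variation.** The 24-month variance/mean ratio is V = 1 + μk. True SE / model SE is √(2V) with three stacked periods and √V with two unclustered periods.

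| V | Three periods: SE ratio, coverage | Two periods: SE ratio, coverage |
|---|---|---|
| 1.0 | 1.41, 83% | 1.00, 95% |
| 2.0 | 2.00, 67% | 1.41, 83% |
| 2.7 | 2.32, 60% | 1.64, 77% |

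Over the full assumed range, the three-period SE ratio runs from 1.41 to 3.16 and coverage from 83% to 47%.

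**Step 3: a plausible V.** Only children in relapse are enrolled, so the relevant part of the Sample size statement is that half of relapsing children become frequent relapsers. Assume, for illustration, that half the children relapse once a year and half three times. The 24-month means are then 2 and 6, the overall mean is 4 and the variance of the means is 4, so V = 1 + 4/4 = 2.0. A gamma distribution of rates with 1.6 relapses a year (μ = 3.2) and k = 0.5 gives V = 1 + 3.2 × 0.5 = 2.6.

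**Step 4: simulated type I error at V of about 2.0-2.7, 72 per arm.**

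- Three stacked periods, plain Poisson: about 34-40%.
- Periods 1 and 2 only, plain Poisson: about 18-22%.
- Periods 1 and 2 only, SEs clustered on the child: about 5-6%.
- Periods 1 and 2 only, negative binomial without clustering: 7.7-10.3%.

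The treatment estimate was the same in the stacked and two-period fits. Clustering on the child also restored the correct SE in the stacked fit (0.118 at μ = 2, k = 0), which shows that the error lies in the variance and not in the estimate.

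**The case against.** **The 0-24 month window may be for reporting only.** The SAP does not say outright that the three counts are stacked, and the outcome definition, with its cut-offs at 12 and 24 months, fits a reporting window. A reader might infer that every relapse is certainly counted twice. The text supports only that this follows from its plain reading. On the reporting-window reading the factor of 1.41 goes, but the within-child correlation remains unaddressed.

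**Silence is not exclusion.** The SAP does not rule out a clustered or GEE fit. That is fair: the correlation is unaddressed rather than knowingly ignored. But an analyst who fits the model as named would get the uncorrected standard errors.

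**The 80%/50% figures describe patients in general.** A reader might take the 20% who never relapse as evidence of a near-zero-rate group in this trial. Eligibility requires a current relapse, so those children cannot be enrolled, and the 20% is not used for the argument here. The 50% split among relapsing children still makes between-child variation likely.

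**The sizes rest on assumed rates.** This stands for everything beyond the factor of 1.41. The simulations also left out maintenance therapy, sex and age, which could absorb part of the variation.

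**It is a secondary endpoint.** This stands, and it limits the weight of the point.

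**Conclusion.** The point holds, conditionally on how the period factor is used. With three stacked periods, the standard error is too small by a factor of at least 1.41, coverage is at most about 83% and type I error is at least about 16-17%. With two periods only, double counting disappears, but plain Poisson still makes no allowance for variation between children. The larger figures (34-40% stacked, 18-22% with two periods) depend on an assumed variance/mean ratio of 2.0-2.7, which the SAP does not supply.

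A reader might also infer that the estimated treatment effect is wrong or that the primary result is affected. Neither is supported: the estimate is not biased in the balanced case, and the time-to-relapse analysis does not use this model. What is wrong is the standard errors, CIs and p-values of one secondary endpoint, which should be corrected before analysis.

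**What to change.** Reword the analysis of the number of relapses as follows:

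1. In the model with a period term, use only the non-overlapping periods 0-12 and 12-24 months.
2. Fit Poisson GEE or negative binomial regression, in either case with robust standard errors clustered on the child. Negative binomial on two rows per child without clustering is not enough.
3. Include log follow-up time as an offset, since the Missing data section keeps partial follow-up.
4. Take the 0-24 month rate ratio from a separate model with one row per child: negative binomial, or Poisson with robust standard errors.

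The cost is a change of SAP wording. No new data are needed, and the SPSS generalized linear model and GEE procedures cover it. The Blinding section allows final SAP amendments at the blind review. The CIs will be wider, but they will have close to their stated coverage.
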